12.10 Liability and Insurance

The sponsor will underwrite any legal liability for injuries caused to participating persons and arising out of this research performed strictly in accordance with the scientific protocol as well as with applicable law and professional standards.

12.11 Ongoing Access to Study Drug

According to the Declaration of Helsinki (Revision 2008), at the conclusion of the study, every subject entered into the study should be assured of access to the best proven, in this case, therapeutic method identified by the study. As such, this study is assessing the efficacy of a combination therapy. If this therapy should be deemed to be beneficial to the subject, the Sponsor will provide the subject with access to the study drug from the time at which the study has concluded through to either the Study drug being registered for use in Australia, the application for registration in Australia is rejected by the TGA, the Sponsor determines that the Study drug will not succeed in gaining registration, or through further studies determines that it is not the best proven therapy.

13. ADMINISTRATION

13.1 Case Report Forms (CRFs)

A CRF will be provided by the sponsor for each subject.

All protocol-required information collected during the study must be entered by the investigator, or designated representative, in the case report form. Details of case report form completion and correction will be explained to the investigator. If the investigator authorises other persons to make entries in the case report form, the names, positions, signatures, and initials of these persons must be supplied to the sponsor.

The investigator, or designated representative, should complete the case report form pages as soon as possible after information is collected, preferably on the same day that a study subject is seen for an examination, treatment, or any other study procedure. Any outstanding entries must be completed immediately after the final examination. An explanation should be given for all missing data.

The completed case report form must be reviewed and signed by the investigator named in the study protocol or by a designated sub-investigator.

The sponsor will retain the originals of all case report forms. The investigator will retain a copy of all completed CRF pages.

13.2 Monitoring

Monitoring and auditing procedures developed by the sponsor (or delegate) will be followed, in order to comply with GCP guidelines. On-site checking of the case record forms for completeness and clarity, cross checking with source documents, and clarification of administrative matters will be performed.

13.2.1 Study monitoring

Monitoring will be done by personal visits from a representative of the sponsor (site monitor) who will review the case record forms and source documents. By frequent communications (letter, telephone and fax), the site monitor will ensure that the investigation is conducted according to protocol design and regulatory requirements.

All unused study materials are to be returned to the sponsor after the clinical phase of the trial has been completed.

13.3 Source Data Verification and On-site Audits

Regulatory authorities, the HREC, and/or the sponsor's clinical quality assurance group may request access to all source documents, case record forms, and other study documentation for on-site audit or inspection. Direct access to these documents must be guaranteed by the investigator, who must supply support at all times for these activities.

13.4 Archiving

All study documents (including source documents) will be archived for a period of 15 years following completion of the study (according to the requirements of GCP). The archive boxes must be labelled clearly to identify the study/subject/documents as well as the 15-year archiving requirement.

The Investigator must store these in a secure, limited access area.

13.5 Use of Study Findings

All information concerning the product as well as any matter concerning the operation of the sponsor such as clinical indications for the drug, its formula, methods of manufacture and other scientific data relating to it, that have been provided by and are unpublished, are confidential and must remain the sole property of the sponsor. The investigator will agree to use the information only for the purposes of carrying out this study and for no other purpose unless prior written permission from sponsor is obtained.

The original case report forms will be stored for 15 years completed as part of the study.

By signing the study protocol, the investigator agrees that the results of the study may be used for the purposes of national and international registration, publication, and information for medical and pharmaceutical professionals. If necessary, the authorities will be notified of the investigator's name, address, qualifications, and extent of involvement.

13.6 Report and Publications

The sponsor will prepare the final report on the study 12-16 weeks after the close of the database and the close out meeting. The investigator (or co-investigator) will be required to

sign a statement that he/she has read the report and confirms that, to the best of his or her knowledge, it accurately describes the conduct and results of the study.

The Final Study Report may be made available to the HREC, at the HREC's request. The HREC Final Study Report will be sent to the HREC once the study has been closed. This document includes information on how the study was performed, number of AE's and SAE's and their resolution status.

The findings of the study may be published in a scientific journal or presented at a scientific meeting. Before submitting the results of the study for publication or presentation, the investigator will allow the sponsor 30 days in which to review and comment on the manuscript. For any publication manuscript prepared by the sponsor, the sponsor reserves the right to select the investigators who will be authors and review the manuscript. The sponsor will allow the selected investigators 30 days for full review of the manuscript before publication.

14. STUDY DURATION AND DATES

The duration of this study is to be a period of 24 months with subject recruitment proposed to start in Q1 2016 and ending in Q2 2018.

APPENDIX 1: STUDY LABORATORY TESTS

Blood Examination

BIOCHEMISTRY

LFTs

Albumin
Bilirubin
GGT (Gamma Glutamyl Transferase)
ALP (Alkaline Phosphatase)
ALT (Alanine Aminotransferase)
AST (Aspartate Aminotransferase)

CK-MB

High sensitivity Troponin T

Hs-CRP

Electrolytes, urea, creatinine

Serum lipids

HAEMATOLOGY

Haemoglobin
Red Cell Count
Haematocrit
MCV
MCH
MCHC
RDW
WCC
Neutrophils
Lymphocytes
Eosinophils
Basophils
NRBC
Platelets
ESR

Chlamydomphila pneumoniae macrophage cultures

Chlamydomphila pneumoniae titers

Chlamydomphila pneumoniae DNA detection by LAMP (exploratory)

APPENDIX 2 – LIST OF RESTRICTED MEDICATIONS

The below list includes the trade names of restricted medications. However it cannot be assumed that this is a complete list. As such, all concomitant medications should be checked, regardless of their presence/absence on the below list.

INR monitoring will be conducted on any participant taking Warfarin

Closer clinical and blood-test monitoring on those with the following concomitant therapies:

- Calcium channel blockers
- Beta blockers
- Amiodarone
- Anti-depressants
-

Statins and ezetimibe can cause abnormal liver function tests. In such patients slower initiation of antibiotics may be required

Absolutely Contraindicated

- Colchicine (Azithromycin interaction)

Relatively Contraindicated

- Theophylline
- Terfenadine
- Tolterodine

APPENDIX 3: SERIOUS ADVERSE EVENT REPORT FORM

- Initial Report: Date ___/___/___
- Follow-up Report (1): Date ___/___/___
- Follow-up Report (2): Date ___/___/___
- Follow-up Report (3): Date ___/___/___

SITE INFORMATION					
Protocol No.	Site No.	Investigator Name	Reporter Name	Reporter Phone No.	Sponsor
PATIENT INFORMATION					
Patient No.	Patient Initials	D.O.B	Sex	Height (at time of event)	Weight (at time of event)
		___/___/___	Male / Female	cm	kg
EVENT					
Event Onset Date	Resolution Date	Severity of Event	Relationship to Product	Treatment Required	Outcome of Event
___/___/___	___/___/___	 Mild  Moderate  Severe	 Definitely related  Probably related  Possibly related  Unlikely related  Not related (If cause known, specify _____)  Unassessable	 No  Yes (If yes, specify in comments and con meds)	 Recovered without treatment  Recovered with treatment  Event ongoing without treatment  Event ongoing & controlled with treatment  Event ongoing & not controlled with treatment  Patient died
Did the SAE occur during Lead-In (Pre-randomisation) Phase					YES / NO
EVENT CATEGORY (Check all that apply)					
 Fatal  Life Threatening  Required Inpatient Hospitalisation or Prolongation of Existing Hospitalisation  Resulted in Permanent or Significant Disability  Congenital Anomaly / Birth Defect		 Other Significant Medical Hazard (Medically Important)  Necessitates medical or surgical intervention to preclude permanent impairment of body function / structure  Necessitates medical or surgical intervention to relieve unanticipated, temporary impairment of body function  Results in permanent impairment of a body function or permanent damage to a body structure			

STUDY DRUG INFORMATION						
Product Name	Form	Strength	Dose	Route	Date of First Intake	Date of Last Intake

					__/__/__	__/__/__
					__/__/__	__/__/__
					__/__/__	__/__/__
					__/__/__	__/__/__

ACTION TAKEN

- None
- Dose Reduced to : _____ Date: ____/____/____
- Dose Increased to : _____ Date: ____/____/____
- Drug Interrupted : Date: ____/____/____
- Drug Restarted : Date: ____/____/____
- Drug Discontinued Permanently

CONCOMITANT MEDICATIONS
(Exclude study drugs and medications used to treat this SAE)

Medication Name	Form	Strength	Dose	Date Started	Date Stopped	Reason
				__/__/__	__/__/__	
				__/__/__	__/__/__	
				__/__/__	__/__/__	
				__/__/__	__/__/__	
				__/__/__	__/__/__	

RELEVANT SAE LABORATORY DATA

Test	Date of Baseline Test	Value of Baseline Test	Date of Study Test	Value of Study Test
	__/__/__		__/__/__	
	__/__/__		__/__/__	
	__/__/__		__/__/__	
	__/__/__		__/__/__	
	__/__/__		__/__/__	
	__/__/__		__/__/__	

APPENDIX 4: DEFINITIONS OF CAUSALITY AND SEVERITY OF ADVERSE EVENTS

1. *Criteria for determining relationship of clinical adverse events to test drugs*

a. **Not Related**

This category applies to those adverse experiences that, after careful consideration, are clearly and incontrovertibly due to extraneous causes (disease, environment, etc.).

b. **Unlikely** (must have two of the following)

In general, this category can be considered applicable to those adverse experiences, which, after careful medical consideration at the time in which they are evaluated, are judged to be unrelated to the test drug. An adverse experience may be considered unlikely related if or when:

- i. It does not follow a reasonable temporal sequence from administration of the drug.
- ii. It could readily have been produced by the participant's clinical state, environment or toxic factors, or other modes of therapy administered to the patient.
- iii. It does not follow a known or expected response pattern to the test drug.
- iv. It does not reappear or worsen when the drug is re-administered.

c. **Possibility** (must have two of the following)

This category applies to those adverse experiences which, after careful medical consideration at the time they are evaluated, a connection with the study medication appears unlikely but can not be ruled out with certainty. An adverse experience may be considered possibly related if or when:

- i. It follows a reasonable temporal sequence from administration of the drug.
- ii. It could not readily have been produced by the participant's clinical state, environment or toxic factors, or other modes of therapy administered to the patient.
- iii. It follows a known response pattern to the test drug.

d. **Probably** (it must have three of the following)

This category applies to adverse experiences which, after careful medical consideration at the time they are evaluated, are felt with a high degree of certainty to be related to the study medication. An adverse experience may be considered probably related if or when:

- i. It follows a reasonable temporal sequence from administration of the drug.
- ii. It could not readily have been produced by the participant's clinical state, environment or toxic factors, or other modes of therapy administered to the patient.
- iii. It disappears or decreases on cessation or reduction in dose. There are important exceptions when the adverse event does not disappear upon discontinuance of the drug, yet drug-relatedness clearly exists; eg. a) bone marrow depression, b) fixed drug eruptions, and c) tardive dyskinesia.
- iv. It follows a known response pattern to the test drug.

e. **Definitely** (Must have all four of the following)

This category applies to those adverse experiences which the investigator feels are incontrovertibly related to the study medication. An adverse experience may be considered definitely related if or when:

- i. It follows a reasonable temporal sequence from administration of the drug.
- ii. It could not readily have been produced by the participant's clinical state, environment or toxic factors, or other modes of therapy administered to the patient.
- iii. It disappears or decreases on cessation or reduction in dose and recurs with re-exposure to the drug. This is not to be construed as requiring re-exposure to the drug. However, a category of definitely related can only be used when recurrence is observed.
- iv. It follows a known response pattern to the test drug.

3. *Criteria for rating the severity of adverse events:*

“Adverse Events”: Any adverse change or experience from the patient’s baseline (pre-treatment) condition which occurs during the course of a clinical study, after starting treatment, whether considered treatment related or not. “Treatment” includes all investigational agents administered during the course of the study.

“Severity of adverse events”: All adverse events must be rated on a three-point scale of increasing severity.

- a. **Mild:** symptoms barely noticeable to the patient; does not influence performance or function. Prescription drugs not ordinarily needed for relief of symptoms but may be given because of the personality of the patient.
- b. **Moderate:** symptoms of a sufficient severity to make patient uncomfortable; performance of daily activities is influenced; patient is able to continue in the study; treatment for symptoms may be needed.
- c. **Severe:** symptoms cause severe discomfort. May be of such severity that patient can not continue performance of daily activities. Severity may cause cessation of treatment with study drugs; treatment for symptoms may be given and/or patient hospitalised.

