The experience with long term use of a combination of three antibiotics in *Mycobacterium avium paratuberculosis* and Crohn's disease has been largely in younger subjects who did not receive anti-platelet agents as concomitant therapies, and thus, macrolide anti-platelet agent interactions have not been observed. In the proposed group of subjects with CHD disease, clarithromycin has a known interaction with anti-platelet agents and therefore in this group, clarithromycin will be substituted by azithromycin, a similar macrolide that demonstrates the same intracellular activity against *C.*

pneumoniae but does not exhibit such interaction with anti-platelet agents. The azithromycin dose will be reduced due to its longer half-life, resulting in longer bioavailability duration in the body. Due to reported occasional QT-prolongation at high doses of azithromycin, ECG monitoring of the QT-interval will be carried out.

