8. ADVERSE EVENTS

8.1 Definitions

8.1.1 Adverse event

The term adverse event (AE) covers any sign, symptom, syndrome, or illness that appears or worsens in a subject during the period of observation in the clinical study and that may impair the well being of the subject. The term also covers laboratory findings or results of other diagnostic procedures that are considered to be clinically relevant (e.g. that require unscheduled diagnostic procedures or treatment measures, or result in withdrawal from the study). Undesirable experiences including intercurrent events (or diseases), drug reactions and clinical abnormalities or clinically significant laboratory test abnormalities, which occur during the course of a trial, are also included.

The AE may be:

- A new illness
- Worsening of a sign or symptom of the condition under treatment or of a concomitant illness
- An effect of a comparator drug
- Unrelated to participation in the clinical study
- A combination of one or more of these factors

Thus, no causal relationship with the study medication is implied by the use of the term “adverse event”. Surgical procedures themselves are not adverse events; they are therapeutic measures for conditions that require surgery. The condition for which the surgery is required may be an adverse event. Planned surgical measures permitted by the study protocol and the conditions leading to these measures are not adverse events. (See Appendix 4 - Definitions of causality and severity of adverse events).

Interviews concerning AEs must be conducted with regard to objectivity. Questions must be phrased so that they do not, by suggestion, lead the subject into giving information, which is not valid. The investigator must carefully evaluate the response and comments of the subject in order that he or she may judge the true nature and severity of the adverse event.

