8.2.2 Serious adverse event

A serious adverse event (SAE) is any AE that occurs at any dose of the study medication or at any time during the period of observation that:

- Results in death
- Is immediately life threatening
- Requires or prolongs hospitalisation
- Results in persistent or significant disability or incapacity
- Occurs with overdose
- Involves cancer
- Involves congenital anomaly/birth defects
- Is medically important
- Requires medical intervention to prevent permanent impairment or damage

“Medically important” events are events that may not be immediately life threatening or result in death or hospitalisation, but may jeopardise the subject or require intervention to prevent one of the other outcomes listed in the definition above. Examples of such events are intensive treatment in an emergency room for allergic bronchospasm, blood dyscrasias or convulsions that do not result in hospitalisation, or development of drug dependency or drug abuse. Such events should be documented and reported as SAEs.

Events “requiring medical intervention to prevent permanent impairment or damage” are events where the investigator believes that medical or surgical intervention is necessary to preclude permanent impairment of a body function or to prevent damage to a body structure.

As there is an overlap between the terms “medically important event” and events requiring medical intervention to prevent permanent impairment or damage, it is left to the discretion of the investigator to select the more applicable of the two criteria when completing the “Serious adverse event form”.

All AEs observed by the investigator or reported by the subject whether or not considered related to the test medication will be followed up by the investigator until resolution, stabilisation or lost to follow up.

All AEs will be reported in the adverse event forms of the CRF and assessed by the investigator in terms of severity and relationship to the test medication. The outcome of the adverse event as well as the measures taken as a result of this event will be described in the adverse event form of the case record form.

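### Appendix 4 gives no severity criterion for laboratory or ECG adverse events, and its Moderate grade mixes intensity with the ability to stay in the study

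*Combined protocol and SAP*

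**What the plan says.** Appendix 4 item 3 leaves no event ungraded: "All adverse events must be rated on a three-point scale of increasing severity". The grades are then defined as follows.

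- Mild: "symptoms barely noticeable to the patient; does not influence performance or function".
- Moderate: "symptoms of a sufficient severity to make patient uncomfortable", followed by "performance of daily activities is influenced; patient is able to continue in the study; treatment for symptoms may be needed".
- Severe: opens with severe discomfort. It adds that daily activities may become impossible, that study drug may be stopped, and that the subject may be treated or hospitalised.

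None of the three mentions a laboratory value, a blood count or an ECG interval.

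The definition of an adverse event is wider than the scale. Section 8.1.1 states: "The term also covers laboratory findings or results of other diagnostic procedures that are considered to be clinically relevant". Section 7.2.2.1 likewise has clinically significant out-of-range values recorded as adverse events. The protocol also expects findings of this kind. Section 1.2 says "Due to reported occasional QT-prolongation at high doses of azithromycin, ECG monitoring of the QT-interval will be carried out", and Appendix 2 notes that "Statins and ezetimibe can cause abnormal liver function tests".

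Section 8.2.2 makes the investigator responsible for the severity rating. The serious adverse event form in Appendix 3 offers the same three levels and no other.

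**The concern.** Grading is compulsory, but a whole class of adverse event has no criterion to be graded by. Laboratory and ECG abnormalities are often found by measurement before the subject feels anything. On a scale of felt symptoms the natural default for such a finding is the lowest level, so the severity record would be least informative for events that only testing can reveal.

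The grade also feeds one other classification. Section 8.3 treats a condition already present at first dose as treatment emergent only if its severity or frequency has worsened since. If a silent abnormality is Mild at baseline and still Mild at a much worse value, the definition may not be triggered.

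The second problem is separate. By making ability to carry on in the study part of Moderate, the scale brings disposition into a measure of intensity. Two events of equal intensity can then be graded differently because one subject could continue and the other could not.

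Safety is in the study title and in secondary objective 3 of Section 2.2, so the severity record should be reliable.

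**Working it through.** The plan states no figure on this point and no arithmetic applies. The check is to apply the grade wording literally to the kinds of event the protocol says will be recorded.

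| Event | Mild | Moderate | Severe | Result |
|---|---|---|---|---|
| A. Clinically significant liver-test rise or long QT, no symptoms | Nearest fit, though also worded by symptoms | Fails: no discomfort | Fails: no severe discomfort | Mild by default, or no fitting grade |
| B. As A, but the finding leads to withdrawal from the study (an example of relevance given in Section 8.1.1) | Nearest fit | Fails twice: no discomfort, and not able to continue | Fails: no severe discomfort | Lowest grade or none, although participation ended |
| C. Uncomfortable symptoms that make the subject unable to continue in the study | Fails: symptoms are more than barely noticeable | Fails on the continuation condition only | Opening criterion not met, but the only level left above Moderate | Outside Moderate; likely moved to Severe |
| D. Uncomfortable symptoms affecting daily activities; subject stops study drug but could stay in the study | Fails | Met | Not needed | Moderate remains available |

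**Treatment-emergent step.** Take a subject with a liver-test abnormality at first dose, which is plausible given the Appendix 2 remark on statins and ezetimibe.

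1. The abnormality was already present, so the first limb of the Section 8.3 definition does not apply.
2. The second limb needs a worsening in severity or frequency.
3. Frequency has no obvious meaning for one continuing laboratory abnormality, so severity has to carry the test.
4. On a symptom-only scale, a silent rise goes from Mild to Mild. An investigator who reads severity through Appendix 4 would see no worsening.

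**Where the grade is not used.**

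- Immediate reporting under Sections 8.3 and 8.4 turns on seriousness.
- Section 8.2.2 defines seriousness independently of symptoms and includes medically important events.
- Section 9 does not tie withdrawal to a grade.
- Section 11 contains no analysis or rule based on severity.

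**Whether disposition is recorded elsewhere.** The Appendix 3 form has separate fields for treatment required, action taken and event category, the last including hospitalisation. Section 8.2.2 has outcome and measures taken described on the adverse event form of the CRF. Section 9 has any stated reason for withdrawal recorded. Removing these elements from the grades therefore loses no information.

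**The case against.** The best defence is that the text does not force a wrong grade. A reader might infer that silent toxicity must be rated Mild. No passage says so: Mild is itself worded by symptoms, performance and function are undefined, and the investigator decides. This stands, and Mild is a likely default rather than a rule. It does not remove the gap, because an investigator who has to choose one of three levels is given nothing to choose by.

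A reader might also infer that anyone who drops out for poor tolerability is barred from Moderate. That goes too far. The condition is ability to continue, so a subject who could have continued and chose to leave still meets it. Section 9 is framed as withdrawal from study medication and seeks follow-up and end-of-treatment procedures afterwards, so stopping drug is not the same as being unable to continue in the study. The Severe wording on stopping drug is permissive. Only case C is affected.

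The consequences are also limited. Section 7.2.2.1 has abnormal values noted in the CRF and followed until stable, and a dangerous silent finding can still be serious as medically important. Section 8.5 specifies no severity table for the DSMB. Section 13.6 describes the ethics committee's final report by how the study was performed and by the number and resolution of events, not by grade. All of this stands and limits the point to the accuracy of the severity record and what is derived from it.

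Nor should the named hazards be overstated. Section 1.2 ties QT prolongation to a study drug, whereas Appendix 2 attributes abnormal liver tests to statins and ezetimibe. The Section 8.2.2 phrase "blood dyscrasias or convulsions that do not result in hospitalisation" is a generic example of a medically important event, not a hazard singled out for monitoring. That such an event could be both serious and Mild is not a defect in itself, since seriousness and severity are meant to be different axes.

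**Conclusion.** The point holds in limited form and should be corrected. Appendix 4 item 3 makes grading compulsory but gives no criterion for laboratory or ECG adverse events. Symptomless ones will probably be recorded as Mild, and silent worsening of a baseline abnormality may be missed as treatment emergent. Moderate also excludes an event of moderate intensity that makes the subject unable to continue, which mixes intensity with disposition. The effect reaches recorded severity, treatment-emergent classification and any safety summary by grade, and goes no further.

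I give no count of affected events. The documents state no rate for symptomless findings and no breakdown of reasons for drop-out. Section 3 speaks of approximately 80 subjects being approached and an assumed 25% drop-out. It does not say that 80 will be randomised or why subjects would leave, so a number of mis-graded events built on those figures would rest on invented rates. Nor do the documents support the inference that severity would be distorted mainly in one arm.

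The conclusion assumes that investigators follow the Appendix 4 wording and that no grading guidance exists outside the document. The appendix numbering runs from item 1 to item 3 in the text available; I draw nothing from that gap.

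**What to change.** Amend Appendix 4 item 3 and the matching CRF guidance.

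1. Grade adverse events that are laboratory or ECG findings from the measured value, relative to the reference limit and the subject's baseline. Use one published toxicity table, which the sponsor names in the protocol together with its mapping to the three levels. Where the event also causes symptoms, record the higher of the value-based and symptom-based grades. No thresholds are proposed here.
2. Remove from the grade definitions the Moderate condition on continuing in the study and the Severe references to stopping study drug and to hospitalisation. Keep these facts in the existing fields for action taken, measures taken and event category.

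The cost is wording and a short briefing for sites, with no new visits or samples. Laboratory values are already scheduled at Visits 1 to 3. For the ECG, the documents disagree on Visit 2: Section 7.1.2 lists one, while the Study Schedule and Section 7.2.1.4 give only Visits 1 and 3. These passages need to be reconciled so that it is clear when a QT value will exist to be graded. The downside is that some laboratory or ECG events will be reported as Moderate or Severe instead of Mild.
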